#### Active Comparators Cohort

Subjects in the active comparator cohort will include those subjects in the *all mRNA vaccinated first dose population* (ie, received at least 1 dose of an mRNA vaccine within the study period, and this was their first COVID-19 vaccine dose) that fulfil *all* the following inclusion criteria:

- Have at least 12 months of data available before the index date
- Have no record of vaccination with any other COVID-19 vaccine on or before the index date

The **index date** is the date when a subject received the first identified Comirnaty dose or the first identified Spikevax dose within the study period.

All subjects in the active comparator cohort will be **matched** to subjects in the AZD1222 vaccinated cohort on index date (by  $\pm 2$  weeks), age ( $\pm 2$  years), sex, region, prior diagnosis of COVID-19, and status according to the 5 special populations. Matching will be done with replacement at a ratio of 1:1. The same matching approach will be used for the comparative analysis with the 2 doses population using as **index date** the date when a subject received the second consecutive dose of Comirnaty or Spikevax within the study period.

Note that the distribution for matching covariates was driven by the vaccination policies that steered mRNA and AZD1222 vaccines into specific age and special population categories that varied over time. Where pre-matching populations are deemed significantly different, the suitability of this analysis will be reconsidered as the ability to make comparative inference on the safety profile is limited to a specific sub-population that may not be representative of the general AZD1222 and active comparator populations. To examine this risk, a pre-matching feasibility assessment of cohort comparability will be performed (see section 9.7.3.4).

### Historical Comparators Cohort

A potential comparator subject (**historical comparators**) identified during the period between 2017 and 2018 will be eligible to be matched from the date the subject met all the following inclusion criteria:

- Had at least 12 months of prior data available.

The **index date** for the historical comparators will be same day and month of the AZD1222 index date minus 3 years (subjects from 2018) or 4 years (subjects from 2017)—an approach that intends to address seasonality.

Subjects will be **matched** to AZD1222-vaccinated subjects on age ( $\pm 2$  years), sex, region, and status according to the 5 special populations. Matching will be done with replacement at a ratio of 1:1.

Whether all potential comparators, or only a sample, will be included in the selection of the comparator cohorts will depend on the data governance rules and data management capabilities of each research partner, which is still to be determined. The SAP will document this decision, along with other details about matching criteria.

### Exclusion Criteria

The following exclusion criterion will be considered in all the cohorts:

[figure not shown]
- For each AESI, subjects (in any matched cohort) who had a specific AESI (Table 3) during the look-back period before the index date will be excluded from the cohort for the analysis of that specific AESI, but not from the cohorts for analysis of other AESIs.
  - If a subject had a specific AESI between the index date and the start of the risk window or had any censoring criteria within this time period, the subject will be excluded from the analysis of that specific AESI.

The number of subjects in the *all AZD1222 vaccinated first dose population* and in the *all mRNA vaccinated first dose population* excluded because they had no matches will be described. Similarly, the number of subjects in the initial pool of potential concurrent

unvaccinated comparators and historical comparators that fulfil the inclusion criteria but are excluded because they had no matches will be described.

In the analysis of a specific AESI, if a subject in the *AZD1222 matched cohort* is excluded due to having a prior history of that specific AESI, all its matched subjects will also be excluded from that analysis. Analogously, if the matched subject in the *concurrent unvaccinated comparator* matched cohort or in the *active comparator* matched cohort or in the *historical comparator* matched cohort is excluded, then the corresponding subject in the *AZD1222 matched cohort* will also be excluded from the analysis of that specific AESI.

**Figure 2** Assembly of Study Cohorts

[figure not shown]

Note: The process illustrated here will be conducted separately in each data source. Index date refers to the date of the first dose of AZD1222 for each vaccinee and for each unvaccinated comparator subject (minus 3 or 4 years for each matched historical control) or the date of the first dose of an mRNA vaccine for each active comparator subject. Subjects in the concurrent unvaccinated cohort will be allowed to enter the AZD1222 or the active comparator cohort if they later fulfil specific cohort entry criteria.

Note that the comparative analysis between AZD1222 and active comparator cohorts will be conducted among vaccinees who have received 2 doses. COVID-19, coronavirus disease 2019; SCRI, self-controlled risk interval.

Figure 3 illustrates cohort design concepts of eligibility, index dates, and the potential to move from a comparator (unexposed) to the exposed cohort.

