### 9.1.1 Retrospective Cohort Design

A retrospective cohort of exposed subjects will be selected. Subjects will enter the exposed cohort upon their first vaccination with AZD1222. Subjects in the AZD1222 cohort will be matched, as applicable, to 3 different comparator cohorts: concurrent unvaccinated subjects, active comparators (ie, subjects vaccinated with an mRNA vaccine against COVID-19), and historical comparators enrolled in the study data sources during the pre-pandemic period (ie, from 2017 to 2018). The AZD1222 cohort will be matched, as applicable, independently to the 3 different comparator cohorts on calendar date of vaccination, age, sex, region, prior COVID-19, and status according to each of the 5 special populations (Section 9.2.1.2). Propensity scores (PSs) will be used to address confounding, balancing multiple covariates such as comorbidities, markers of healthcare utilisation and comedication between the vaccinated and the different comparator cohorts (Austin 2014, Webster-Clark et al 2021). Relative risk will be the main measure of effect, which will be estimated using incidence rate ratios (IRRs), prevalence proportion ratios (PPRs), or hazard ratios (HRs), depending on the analysis and outcome. Absolute risk difference measures will include incidence rate differences, prevalence proportion differences (PPD), and  $1 - KM^2$  differences.

In the cohort study, the initial plan was to use concurrent, rather than historical, comparator (unvaccinated) subjects because they are at risk for COVID-19, and COVID-19 may function as an important covariable in the analyses of several of the safety endpoints. Moreover, both healthcare-seeking behaviours and healthcare delivery during the pandemic differ from those during the pre-pandemic era. The potential challenge with this approach is that during the pandemic, concurrent unvaccinated subjects in the comparator group may themselves become vaccinated over time. Results from Interim Reports 1 and 2 confirmed that the duration of follow-up among concurrent unvaccinated subjects was short (median, < 2 months in all data sources) and probably not long enough to evaluate AESIs with unknown risk window—(those with a risk window that ends at 180 or 365 days). Thus, additional comparators for whom the follow-up is expected to be longer were requested by the PRAC and have been added to the

---

[figure not shown]
 KM, Kaplan-Meier estimate.

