**Table 3 Adverse Events of Special Interest and Other Safety Concerns**

Adverse event	Suitable for SCRI analysis according to ACCESS protocol template a	Risk interval after index date (days)	Clean look-back interval (days) k
Acute aseptic arthritis	Yes	1-42 b	365
Fibromyalgia	No d	91-365 h	365
Rhabdomyolysis	No d	1-42 b	365
Chronic fatigue syndrome/ME/PVFS	No d	183-365 i	365
Erythema multiforme	No f	1-365 e	365
Chilblain-like skin lesions	No f	1-365 e	365

a Suitability according to ACCESS protocol template entitled “Safety evaluation of COVID-19 vaccines in electronic healthcare databases.” See Section 9.1.2 and Section 9.2.1.3 for additional information on SCRI design.

b Risk interval based on consensus definition from the AESI Working Group of Vaccines Europe, March 2021.

c Based on Lee et al (2011) or COVID-19 Vaccine Safety Surveillance: Active Monitoring Master Protocol (FDA 2020).

d Not addressed in ACCESS protocol template but is deemed not suitable for one or more of the following reasons: onset may be gradual, the diagnosis date may substantially lag the onset of symptoms, or the risk period is not clearly established.

e No consensus evidence for a risk period was identified; defaults to 1 year following index date.

f ACCESS protocol template indicates “yes,” or SCRI may be suitable if a purported risk period can be identified, which is not yet known for this AESI. Absent such information, deemed not suitable.

g Sensitivity analyses will evaluate alternative risk windows. For TTS, they will be 1-14, 1-21, and 1-28 days after the index date. For thrombocytopenia with bleeding, the alternative risk window will be 1-28 days after the index date, following Pottegård et al (2021).

h No consensus evidence for a risk period was identified. However, because symptoms need to be present for at least 3 months before subjects qualify for the diagnosis (Arnold et al 2019), the start of the risk window was set to 91 days after the index date.

i No consensus evidence for a risk period was identified. However, because chronic fatigue needs to be present for at least 6 months before subjects qualify for the diagnosis (IOM 2015), the start of the risk window was set to 183 days after the index date.

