It is expected that the subject groups targeted for vaccination will change over the course of the study in all countries. Matching on calendar date and age will address this concern and may also reduce potential confounding due to changing patterns of SARS-CoV-2 infection (including the potential for herd immunity to develop over time) and for changes in healthcare-seeking behaviours that have been observed during the pandemic. Being unvaccinated may also be related to lifestyle choices that are difficult to measure. It is unlikely that the data sources will have information on all potential confounders. Failure to account for variables that are unmeasured (or imperfectly measured) may lead to **residual confounding** ([Webster-Clark et al 2021](#)). To address potential confounding, the SCRI, which automatically adjusts for time-invariant confounders, will be used as a secondary approach, and using only postvaccination control periods will avoid the potential bias that use of prevaccination control periods may introduce, as prevaccination health events may affect the probability of exposure.

However, the SCRI design is not well suited to study outcomes with gradual onset, long latency, or risk periods that are not well known.

It is conceivable that over the study period, as more of the population has received vaccines to prevent COVID-19, the population of potential **concurrent unvaccinated comparators will dwindle** or that people who remain unvaccinated may be systematically different from those who choose to be vaccinated. Additionally, the age restrictions on the use of AZD1222 imposed in the UK, Spain, Italy, or the Netherlands, as in most European countries, may make it difficult to find comparable controls for the cohort study. If such a scenario develops, it is proposed to use the SCRI analysis, which includes only exposed individuals, to evaluate vaccine-AESI associations for outcomes that are suitable for this design (Table 3). In the first year of the current study, the availability of comparators and the duration of their follow-up time have been monitored. The results from analyses for the first and second interim reports confirm that the number of concurrent unvaccinated comparators was appropriate; however, the duration of follow-up was too short to evaluate outcomes with long risk windows. For this reason, the protocol was amended to include an active comparator cohort and a historical comparator cohort.

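### For fibromyalgia and chronic fatigue syndrome, the exclusion rules read literally drop AZD1222 vaccinees because their concurrent comparator was censored before the risk window opened

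*Protocol*

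**What the plan says.** Four parts of the protocol meet on this point.

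- **Early exclusion (section 9.2.1.1.3, Exclusion Criteria).** If a subject develops the AESI after index but before its window opens, "or had any censoring criteria within this time period, the subject will be excluded from the analysis of that specific AESI".
- **Pair rule (same section).** A vaccinee excluded for prior history of the AESI takes the matched subjects out too. The next sentence opens with *Analogously* and says that if the matched comparator is excluded, "then the corresponding subject in the *AZD1222 matched cohort* will also be excluded from the analysis of that specific AESI". It names no reason for the comparator's exclusion.
- **Late windows (Table 3 footnotes).** For fibromyalgia, "the start of the risk window was set to 91 days after the index date". For chronic fatigue syndrome, "the start of the risk window was set to 183 days after the index date". Table 3 marks both as unsuitable for the self-controlled design.
- **Comparator follow-up (section 9.1.1).** Interim Reports 1 and 2 showed that "the duration of follow-up among concurrent unvaccinated subjects was short (median, < 2 months in all data sources"). Section 9.9.1 adds that "the duration of follow-up was too short to evaluate outcomes with long risk windows".

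Section 9.7.1 describes follow-up as censored for individuals and not for matched pairs. Section 9.7.10 lists censoring of both pair members as a sensitivity analysis.

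**The concern.** Read together, the first two rules make a vaccinee's place in the analysis depend on another person's course after the index date, chiefly whether the comparator was vaccinated before day 91 or day 183. The vaccinee may still be under observation when the window opens and is lost all the same.

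Two things are at stake in the concurrent comparison. Primary objective 3 describes AZD1222 incidence, and for these two AESIs it would be estimated in a subset selected on a future event in the partner. Precision would also be given up for no gain, because these vaccinees have usable time in the window. Section 9.9.1 itself warns that people who remain unvaccinated may be systematically different, so there is little reason to let their later behaviour decide which vaccinees are counted.

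**Working it through.** **Inputs**

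- Window starts: day 91 and day 183 (Table 3).
- Median concurrent comparator follow-up: under 2 months in all sources (section 9.1.1). I use 60 days as the upper end.
- Matching: 1:1 with replacement (section 9.2.1.1.3).
- Matched AZD1222 subjects (Table 4, Interim Report 2 column): 3,938,490 + 517,015 + 609,842 + 336,889 + 154,858 = 5,557,094.

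**The plan's own figures.** The protocol gives no retained number and no precision figure for either late-window AESI. Its precision tables do reproduce. For Guillain-Barré syndrome with 5 million vaccinees, expected events are a = 5,000,000 × (84/365.25) × 2/100,000 = 23.0 and b = 23.0/3 = 7.67. Then P = Φ(ln 3 / √(1/a + 1/b) − 1.96) = 0.750, against 75% in section 9.5. The AESIs in Tables 5 and 6 have short windows, so those tables do not bear on this point.

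**Step 1: what follows without a model.** If the median is below about 60 days in each source, fewer than half of comparators are still followed at day 60, and no more than that at day 91 or 183. Under the literal pair rule, more than half of pairs are lost from both analyses.

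**Step 2: size under an assumed shape.** Share of pairs retained at day t: S(t) = 0.5^((t/median)^k), where k = 1 is a constant hazard.

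| Median, k | Retained at day 91 | Retained at day 183 |
|---|---|---|
| 60 days, k = 1 | 35% | 12% |
| 60 days, k = 0.5 | 43% | 30% |
| 60 days, k = 2 | 20% | 0.2% |
| 45 days, k = 1 | 25% | 6% |
| 30 days, k = 1 | 12% | 1.5% |

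The first row is a loss of about 65% and 88%. Applied to 5,557,094, it leaves about 1.94 million pairs for fibromyalgia and 0.67 million for chronic fatigue syndrome, if every source has the same median. Only comparator censoring is counted; the vaccinee's own censoring lowers these numbers further.

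**Step 3: reach.** Of the 37 AESIs in Table 3, 12 have windows ending at day 180 or 365. Nine of those open at day 1, and enhanced disease opens at day 14 (0.5^(14/60) = 85% retained in the base case). Only two open late enough for the rule to matter much.

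**Step 4: passages that disagree.**

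- The literal pair rule conflicts with individual censoring in section 9.7.1. It also leaves the pair-censoring sensitivity analysis in section 9.7.10 nothing to test before the window opens.
- Section 8 ties primary objectives 3 and 4 to concurrent comparators and lists historical ones under exploratory objectives. Section 9.2.1.1.3 says all three matched sets address primary and secondary objectives 1, 3 and 4.
- Section 9.2.3.1 ends a concurrent comparator's follow-up at an AZD1222 dose. The footnote to Figure 6 refers to any COVID-19 vaccine other than the one that granted cohort entry.

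**The case against.** The best defence is that *Analogously* carries over the reason in the sentence before it, so that the pair rule covers prior history only. Sections 9.7.1 and 9.7.10 favour that reading: a plan that keeps pair censoring for a sensitivity analysis would hardly delete vaccinees for it in the main one. This may well be the intent. It does not settle the matter, because the sentence has no such limit and stands a few lines below the rule on early censoring. It can be programmed either way.

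The protocol also discloses the short follow-up, adds comparators because of it, and requires exclusions to be reported by cohort and analysis (section 9.7.4). That stands, but nowhere does it say that vaccinees may be dropped for their partner's censoring.

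Four stronger readings are tempting, and the documents do not support them:

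- **That primary objective 3 would be answered only in the retained pairs.** Sections 9.2.1.1.3 and 9.7.6 also plan AZD1222 incidence in the historical-matched set, where COVID-19 vaccination of the comparator cannot cause loss.
- **That only a small remnant is left.** The text fixes only less than half. For fibromyalgia the base case still leaves nearly 2 million pairs.
- **That every vaccinated comparator is removed.** Section 9.2.3.1 and the Figure 6 footnote differ on which dose censors.
- **That the historical comparison should be the main one for 180- or 365-day windows.** Sections 9.1.1 and 9.9.1 give comparability reasons for caution, so this is a trade-off for the sponsor.

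**Conclusion.** The point holds for two AESIs in one of the three comparisons. Taken literally, section 9.2.1.1.3 removes AZD1222 vaccinees from the fibromyalgia and chronic fatigue syndrome analyses when their concurrent comparator is censored before the window opens. The protocol's own median makes that more than half of pairs. The 65% and 88% losses rest on a 60-day median and a constant hazard. With other hazard shapes at that median the loss is 57 to 80% by day 91 and 70 to 99.8% by day 183.

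A reader might infer that the contrast with persistently unvaccinated people is itself an avoidable error. It is not: a comparator censored before the window has no time at risk in it, so under any rule those who remain are the ones who stayed unvaccinated. What can be avoided is the loss and selection of vaccinees, and the ambiguity that permits it.

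**What to change.** 1. In section 9.2.1.1.3, state that pair exclusion applies only to pre-index history of the AESI, and that a subject censored before the window start does not remove the partner.
2. For primary objective 3, estimate AZD1222 incidence of these two AESIs in all matched vaccinees still under follow-up at the window start.
3. Reconcile section 8 with section 9.2.1.1.3 on which comparators serve primary objectives 3 and 4, and section 9.2.3.1 with the Figure 6 footnote on which vaccine dose censors a concurrent comparator.
4. Report the concurrent relative risk for these two AESIs with the number and share of comparators reaching the window start, and describe it as a contrast with people who stayed unvaccinated.

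The cost is wording and some programming, with no new data. The downside is that the arms are no longer pair-matched at the window start, so balance there relies on the propensity-score adjustment. The pair-censored analysis in section 9.7.10 stays as the check. Which comparator is the main one for 180- and 365-day windows remains the sponsor's judgement.

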**Figure 3 Eligibility Criteria and Index Date Definition**

AESI, adverse event of special interest; FU, follow-up; SARS-CoV-2, severe acute respiratory syndrome coronavirus 2.

Subjects in the concurrent unvaccinated cohort will be allowed to enter any of the AZD1222 or active comparator cohorts if they later fulfil specific cohort entry criteria. Subjects in the active comparator cohort will not be allowed to enter the AZD1222 cohort, and vice versa. Subjects in the historical comparators cohort will be allowed to enter the any of the other cohorts if they later fulfil specific cohort entry criteria.

### 9.2.1.2 Special Populations

In addition to the general study population, safety concerns will also be evaluated in prespecified subgroups for which information was deemed missing in the RMP.

- Women who are pregnant or breastfeeding
- Immunocompromised subjects
- Frail subjects with comorbidities (eg, chronic obstructive pulmonary disease, diabetes, chronic neurological disease, cardiovascular disorders)
- Subjects with autoimmune or inflammatory disorders
- Subjects who, at cohort entry, had recently received vaccines to prevent diseases other than COVID-19, such as pneumococcal infection, influenza, and shingles (herpes zoster).

Concepts to identify the special populations are listed in [Appendix C, Annex Table 3](#). Details on algorithms to identify each of these subgroups will be documented in a SAP.

### 9.2.1.3 SCRI Design: Study Population

For each outcome of interest to be evaluated using the SCRI design, the eligible population will include subjects from the AZD1222 cohort who experienced the outcome of interest during the study period. Only selected outcomes with well-characterised risk intervals will be evaluated using this approach (Section 9.3.2). Consistent with other vaccine studies that have used this approach ([Lee et al 2011](#)), events of interest must not have occurred in the recent past in order to distinguish between ongoing care for a historical event and an incident or recurrent event. Accordingly, each outcome will require a “clean” (ie, event-free) interval before the start of observation, which will vary by outcome; proposed specifications for this “clean look-back interval” appear in [Table 3](#). Specific criteria for selection of individuals for the SCRI design will require that:

- The subject received at least one dose of AZD1222
- The subject experienced the event during the risk or control interval
- There is at least 1 day of data accrual, which is used to define the event in the risk and control intervals combined, taking into account the data lag and timing of data extraction.

